3.2.2 Aim 2 Design

In Aim 2, we will conduct semi-structured interviews with select physicians across all study arms to further develop our understanding of what data elements are likely to be the most helpful or significant inputs for the predictive modeling analysis. Each interview will be moderated using a semi-structured interview guide.

Following this, we will develop a regression model to evaluate the association of patient and physician characteristics with a) the likelihood of hypertension treatment intensification overall and b) the responsiveness to the study interventions. Finally, we will construct a model to predict the most likely intervention to elicit treatment intensification given physician demographics, with or without patient data. This model, if successful, could assist health systems in selecting the most appropriate individualized intervention to improve treatment intensification.

3.3 Study Schema

Aim 1

45 PCPs with opportunities to intensify HTN treatment

Conduct consent process.
Baseline questionnaires.

[figure not shown]
[figure not shown]
Block Randomization of PCPs 1:1:1

Arm 1
Academic
E-detailing

Arm 2
Social
Norming

Arm 3
Control

Qualitative interviews

Aim 2

Regression or predictive modeling to:
a) Identify patient and physician clusters
b) Develop responsiveness profiles

3.4 Scientific rationale for study design

The use of a randomized trial design will be able to both provide stronger evidence of causality in the effectiveness of the interventions and allow for empiric derivation of patient and physician characteristics that may influence intervention responsiveness. An observational study design or physician self-report of factors that influence intervention responsiveness are more subject to bias.

3.5 Justification for intervention

Social norming^{10,11} and academic detailing^{10,12,13} interventions are effective tools to change physician behavior and improve hypertension management. However, few studies have evaluated specific patient and physician characteristics that might influence intervention effectiveness. With the results of this study, we hope to be able to target interventions more precisely to increase their effectiveness. This research could provide direct benefit to patients through improved blood pressure control and may increase physicians' awareness and knowledge of hypertension treatment.

3.6 End-of-study definition

The active interventions in aim 1 are expected to last for no more than 6 months, and the post-intervention qualitative interviews will be completed within 2 months after the intervention period is complete. Study data collection for the secondary outcome of blood pressure control will continue for 6 months after the intervention period is complete. Development of the prediction models will be done concurrently during that time. We expect to complete the full study including all analyses by July 2022. Participants will be notified by email of study completion.

3.7 Data sources

Sources of research material, data that will be recorded, when data will be collected

Data regarding patients' medical history, disease control, medication use and health care utilization will be obtained from EHR data, supported by Epic Systems, Inc. The data warehouses for this organization reside in an Oracle 9i environment and consists of the Clarity and Payer databases. The Clarity database is a relational database that contains clinical and financial information from the Epic Suite of products; including the electronic medical record system (EpicCare), the appointment scheduling system (Cadence), the patient accounting

system (Resolute), the patient web portal and the master patient index (Identity). The various tables within the Clarity database are refreshed on a daily, weekly or monthly basis.

Linkages to subjects, access to subject identities

Individually-identifiable data are maintained for patient care purposes within the MGB network and are needed to identify patients for evaluation and to monitor care recommendations by physicians. Without this linkage, we could not fulfill the study's objectives. To protect the confidentiality of these data, only the minimal necessary research staff will have access to personal identifiers. This will be necessary for linking data and contacting physicians. After linkage is completed and study variables are created, all identifiable information will be deleted from the study database. All research staff are properly trained in research management and will be approved by the IRB. All personally identifiable health information will be kept under lock and key.

3.8 Schedule of activities

	Screening	Enrollment	Intervention	Analysis
Identification of eligible physicians	X			
Recruitment of physicians	X			
Consent Process		X		
Physician surveys		X		
Randomization		X	X	
Control & Experimental Interventions			X	
Physician Interviews				X
Primary outcome analysis				X
Predictive modeling analysis				X

4. Study Population

The study will include primary care physicians at MGH.

4.1 Inclusion Criteria

We will include primary care physicians meeting the following criteria:

1. Practicing in primary care at Massachusetts General Hospital.
2. Caring for at least 2 patients: (1) aged 18-79, (2) for whom the recent BP history in the last 18 months is above goal, (3) whose most recent BP at an outpatient visit was above goal, and (4) who did not have their hypertension treatment regimens intensified (dose increase, new medication, or medication exchange) at or since that time. The BP goal will be <140/90 for all patients. To accommodate changes in care delivery that occurred during the COVID surge, outpatient visits will include in-office and virtual visits that had vitals recorded in the EHR the same day. We will exclude patients who were excluded from the hypertension registry, are pregnant or post-partum 6 months, or who are receiving hospice care.

4.2 Exclusion Criteria

Providers will be excluded if they have fewer than 100 patients on their primary care panel or practice less than one session per week. These will be identified using data available from the primary care tableau dashboard and/or the baseline surveys.

Patients will not directly receive intervention, but their clinical parameters will be used to identify eligible providers and upcoming visits with potential opportunities for treatment intensification. For this study, we plan to exclude patients age 80 and older. The SPRINT¹⁴ and HYVET¹⁵ trials enrolled patients aged ≥ 75 and ≥ 80 years respectively and demonstrated the safety and efficacy of blood pressure control to $<130/80$ or $<150/80$, suggesting that medication intensification in this age group is safe and effective. However, another recent trial of de-prescribing for patients >80 years with controlled BP on two or more medications was non-inferior to usual care,¹⁶ suggesting that medication de-escalation may also be appropriate for some patients. In both of these cases, patients who participated in these trials were selected by their physicians who had detailed knowledge of their clinical history and functional status. Because we will not be directly seeking PCP input on patients to include in this trial, and because blood pressure treatment decisions are more nuanced and individualized in this age range, we will exclude patients ≥ 80 years of age from this pilot study.

4.3 Recruitment and retention

We will send email invitations to eligible Primary Care Physicians in the MGH healthcare system. Based on preliminary data, we expect that 100 or more physicians will have at least 2 qualifying patients each and thus will be eligible for the study. Assuming approximately 50% of physicians will agree to participate, we expect to be able to recruit 45 physicians for the study. Our research team includes the Chief of the MGH Division of General Internal Medicine and Associate Medical Director of the Massachusetts General Physician Organization, who will help us achieve our enrollment targets and retention rates.

Physicians will receive \$75 for completion of the baseline surveys. After that time, physicians will receive the interventions and will be able to choose whether or not to incorporate that information into their routine clinical practice, but they will not be required to complete any additional study-specific tasks. We expect that the compensation for their time and minimal study-specific tasks will help ensure retention.

4.3.1 Informed consent considerations

Potentially eligible physicians will be contacted by email and provided with an informational fact sheet. Physicians will then click a link to a RedCap form that will contain the same information in the fact sheet. The fact sheet includes information about baseline questionnaires, potential study interventions (if randomly assigned to one of these arms), and potential for contact at the end of the study to participate in a semi-structured interview. We have allocated approximately 12 weeks for the process of recruitment and consent.

4.3.2 Inclusivity of study subjects

MGH primary care consists of over 200 PCPs who care for more than 200,000 patients across the Boston area. Based on preliminary data, we expect that 100 or more physicians will have at least 2 qualifying patients each and thus will be eligible during the proposed study period. We expect that $\geq 50\%$ of the physicians will agree to participate and that therefore we will be able to recruit 45 physicians for the study. Providers will be excluded if they have fewer than 100 patients on their primary care panel or practice less than one session per week. These will be identified using data available from the primary care tableau dashboard and/or the baseline surveys. The chief of the MGH Division of General Internal Medicine (DGIM), and the Director of Population Health and

Quality for MGH DGIM are engaged in support of this project and will help with study recruitment and retention.

5. Study Interventions

5.1 Therapeutic areas

The focus on the proposed study is uncontrolled hypertension treatment guidelines, defined based upon MGH hypertension treatment quality metrics.

5.2 Study interventions

Eligible physicians who agree to participate will be randomized to one of three treatment groups:

- In arm 1 (academic e-detailing), we will first generate a list of patients who meet the definition for clinical inertia in hypertension care and have an upcoming visit with the PCP in the next few weeks. An MGH clinical pharmacist will then review each patient's chart in advance and provide a personalized recommendation for how to modify the specific patient's antihypertensive regimen based on clinical practice guidelines. For example, the clinical pharmacist might recommend adding an additional medication based on the patient's comorbid conditions and could suggest a starting dose and timeframe for dose escalation. The academic e-detailing recommendations will be sent via an Epic in-basket message for each patient 1-3 days in advance of the patient's scheduled visit.
- In arm 2 (social norming), a report of the physician's hypertension control rates compared to benchmarks will be displayed using principles of social norming. The dashboards will be prepared using EHR data to calculate blood pressure control rates for each individual PCP and for his or her practice mean and practice top performer. Every Thursday, we will send each PCP a list of patients who meet the definition for clinical inertia in hypertension care and have an upcoming visit that week. Every 2-4 weeks, we will additionally attach the physician performance review dashboard.
- In arm 3 (control), physicians will not receive outreach.

5.3 Measures to minimize bias: randomization and blinding

Physicians will be informed about the study and agree to participate using an online consent process through RedCap, and then will be asked to complete a set of behavioral surveys also administered through RedCap. PCPs will then be randomized to one of the two intervention arms

or the control arm. To minimize imbalance between treatment groups, we will use block stratified randomization. Based on the number of sessions per week, providers will be determined to have a small (1-2 sessions), medium (3-4 sessions), or large (5 or more sessions) panel. Within each stratum, we will array physicians into blocks of 3 (note: could also be multiples of 3). All possible balanced combinations of assignment within the block will be allowed in each stratum. Ultimately, within each block and each stratum, physicians will have an equal probability of being assigned to one of the 3 arms.

It will not be possible to blind physicians to the interventions, as they will directly receive either e-consults, dashboards, or no intervention. Because physicians have individual panels, hypertension is typically treated via routine follow-up visits with the PCP, and the interventions are specific to each physician, risk of practice-level contamination is low.

6. Study Assessments and Procedures

6.1 Baseline data

We will collect baseline data using a combination of provider surveys and the EHR. From the provider surveys, we will collect physician age, gender, race/ethnicity, years in practice, practice location, and the behavioral scales detailed below. We will also collect data on providers from the EHR, including, but not limited to: hypertension prescribing trends (frequencies of medications utilized, BP control rates, time to treatment intensification) and information about the PCP's panel such as panel size, demographic characteristics (e.g. age, gender, race/ethnicity), and clinical characteristics (e.g. comorbidities). We will also collect data specific to the patients who meet the definition for clinical inertia and whose visits are targeted by the interventions. This will include sociodemographic data, medical history and comorbidities, baseline resource utilization in prior 12 months (i.e., number of visits), and biometric values (e.g., serum creatinine, systolic/diastolic blood pressures).

The surveys that physicians will complete were selected to capture personality traits and behavioral tendencies that might contribute to clinical inertia or intervention responsiveness.

These surveys will include measures of:

- risk aversion (Physicians' Reactions to Uncertainty Scale)¹⁷
- long and short term orientation (Individual Cultural Values Scale)¹⁸
- conscientiousness (Ten-Item Personality Inventory)¹⁹

- need for cognition (Need for Cognition Scale)²⁰
- resistance to change (Resistance to Change Scale)²¹
- susceptibility to social norms (Social-Norm Espousal Scale)²²
- burnout (Professional Fulfilment Index)²³
- automaticity (Self-Report Behavioural Automaticity Index).²⁴

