7.2 Sample size determination

Because we are selecting specifically for patients with clinical inertia, we expect the control arm rate of medication intensification at the target office visit to be no more than 15%. Assuming an ICC of 0.05, a type I error rate of 5%, and 12 patients per physician over the study period, a sample size of 45 physicians (i.e. 15 per arm) will provide more than 80% power to detect a 15% difference in treatment intensification between each intervention group and control. If the control arm intensification rate is higher than anticipated, we will still be sufficiently powered for reasonable effect sizes (i.e. if the rate of the primary outcome in the control arm was 0.2%, we will be able to detect an effect size of 17%). These data are intended to provide pilot data for larger evaluations, and any positive signal from this pilot trial will help inform next steps. If we have more eligible and

consented physicians than originally anticipated, we will adjust our allocation scheme so that additional physicians are allocated to the control arm to maximize power.

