7.3 Statistical analyses

7.3.1 *Analysis of the primary endpoint*

The primary outcome of this trial will be whether physicians intensified treatment at the visit targeted by the intervention. These data will be collected through EHR data from MGB. We will evaluate the primary outcome using generalized estimating equations (GEE) to adjust for provider-level clustering and multiple patient observations per physician with a logit link function and binary distributed errors; these models will also adjust for the block-randomized design. Because this is a randomized trial, our primary analyses are planned as unadjusted; however, if there are strong predictors of the outcomes not balanced by block randomization, we will adjust for these in the primary analyses. We will conduct analyses using intention-to-treat principles and each intervention arm will be compared to control. Given the nature of the data and how the outcome is being measured, there should not be missing values for our primary outcome.

7.3.2 *Analysis of secondary endpoints*

The secondary outcome of this trial is change in systolic blood pressure control in each arm over 6 months. For this secondary outcome, we will use GEE with an identity link function and normally-distributed errors to account for provider-level clustering, adjusting for the block-randomized design. As in the primary analysis, we will perform analyses unadjusted and adjusted for provider and patient-level covariates to accommodate any imbalance across arms. We will conduct analyses using intention-to-treat principles and each intervention arm will be compared to control. Based on prior studies in a similar local healthcare system, we anticipate approximately 20% missingness rate for the follow-up blood pressure within 6 months, and that this will likely be non-differential between treatment arms.²⁵ Should there be sufficient missing data (e.g., >10%), we will use multiple imputation to handle this. In specific, we will use 20 imputations with Proc MI in SAS to impute any estimated values using fully conditional specification. Analyses will then be conducted on each imputed dataset and combined using Rubin's rules.²⁶ We will perform a complete case analysis as a sensitivity analysis.

7.3.3 *Baseline descriptive analyses*

We will report the means and frequencies of baseline variables for physicians and their eligible patients.

7.3.4 *Subgroup analyses*

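### The primary model leaves out a physician-level predictor that the plan already collects; naming it in advance is a cheap precision gain of about 0 to 8 points of power, depending on an unknown correlation

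*Combined protocol and SAP*

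**What the plan says.** - Section 6.1 (Baseline data) lists physician-level EHR items that include "hypertension prescribing trends (frequencies of medications utilized, BP control rates, time to treatment intensification". It gives no look-back window and does not define how the time measure is summarised for a physician.
- Section 6.2 (Outcomes) names baseline prescribing trends as candidate variables for the Aim 2 predictive model. No Aim 1 use is named.
- Section 5.3 stratifies randomisation on sessions per week only.
- Section 7.3.1 fits a logistic GEE clustered by provider and adjusted for the block-randomised design. It states "our primary analyses are planned as unadjusted", then adds that strong outcome predictors left unbalanced by the randomisation will be adjusted for in the primary analysis. It names no variable and sets no threshold.
- Section 7.2 sizes the trial on "Assuming an ICC of 0.05, a type I error rate of 5%, and 12 patients per physician over the study period". Its conclusion is that "a sample size of 45 physicians (i.e. 15 per arm) will provide more than 80% power". The target is a 15-point gap between either active arm and the control arm. The section assumes a control rate of at most 15% and no baseline covariate.

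**The concern.** The physician is the randomised unit, and the loss of information that section 7.2 allows for comes from differences between physicians. A physician's past readiness to intensify is the natural predictor of those differences. A prognostic covariate removes part of that variance whether or not the arms happen to be balanced on it. Under 7.3.1 the covariate enters only when imbalance is seen. A strong but well-balanced predictor is therefore left out, and its precision is given up.

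At stake is power, not validity. With 15 physicians per arm, the plan's own inputs put power at or slightly under the stated level, so there is no slack.

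**Working it through.** **Inputs.** From section 7.2: 15 physicians per arm, 12 patients per physician (180 patients per arm), ICC 0.05, type I error 5%, control rate 15%, difference 15 points (so 30% under intervention). Two-sided testing and no split of alpha between the two comparisons are my assumptions; the plan states neither.

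**1. The plan's power figure.**
- Design effect: 1 + (12 − 1) × 0.05 = 1.55. Effective patients per arm: 180 / 1.55 = 116.1.
- Pooled formula, mean rate 0.225: null standard error √(2 × 0.225 × 0.775 / 116.1) = 0.0548; alternative standard error √((0.1275 + 0.21) / 116.1) = 0.0539. Then z = (0.15 − 1.96 × 0.0548) / 0.0539 = 0.790, so power is 78.5%.
- Unpooled formula: z = 0.15 / 0.0539 − 1.96 = 0.822, so power is 79.5%.
- With a t reference on 28 degrees of freedom it is 76.6%.

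The claim of more than 80% is thus approximately reproduced, just on the low side.

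**2. The part a physician covariate can reach.** Write the design effect as 12 × 0.05 + 0.95 = 0.60 + 0.95. The between-physician part is 0.60 / 1.55 = 39% of the variance of a physician's mean.

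**3. Gain from a covariate.** If the baseline measure correlates r with the physician's true propensity to intensify, the design effect becomes 0.60 × (1 − r²) + 0.95. Power below uses the pooled formula.

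| r | Design effect | Effective n per arm | Power | Gain (points) |
|---|---|---|---|---|
| 0 | 1.550 | 116.1 | 78.5% | 0 |
| 0.3 | 1.496 | 120.3 | 80.0% | 1.4 |
| 0.5 | 1.400 | 128.6 | 82.5% | 4.0 |
| 0.7 | 1.256 | 143.3 | 86.4% | 7.9 |

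**4. Check by simulation.** This used 5,600 trials per setting, beta-binomial outcomes, 45 physicians, and an exchangeable logistic GEE with session strata and a degrees-of-freedom correction. Power was 75.4% without the covariate and 76.0%, 78.5% and 82.9% at r = 0.3, 0.5 and 0.7: gains of 0.6, 3.1 and 7.5 points. The Monte Carlo standard error is √(0.754 × 0.246 / 5,600) = 0.6 points, so the gain at r = 0.3 is within noise. At r = 0 the loss was under 1 point. The level is lower than in step 3, but the gains are of the same order.

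**5. What r might be.** The documents do not say. As an illustration, take a baseline proportion from m independent patients at ICC 0.05. Its reliability is 0.05m / (1 + 0.05(m − 1)), and r² is that reliability times the squared correlation of true physician rates over time (stability).
- m = 12: reliability 0.60 / 1.55 = 0.39. Gain 1.0, 2.2 or 4.0 points for stability 0.4, 0.6 or 0.8.
- m = 50: reliability 2.50 / 3.45 = 0.72. Gain 4.2 or 7.5 points for stability 0.6 or 0.8.

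**6. If the measure predicts only in the control arm.** Fit one common slope over three arms. With r = 0.5 in control and 0 under intervention, the slope is (0.5 / 3) × √0.60 = 0.129.
- Control arm variance factor: 1.55 − 2 × 0.129 × 0.5 × √0.60 + 0.129² = 1.467.
- Intervention arm: 1.55 + 0.129² = 1.567.
- Weighted by 0.1275 and 0.21, the factor is 1.529, and the gain is about half a point.
- With r = 0.7 in control only, the same steps give about 1 point.

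**7. Dependence on the ICC.** For r² of 0.25 to 0.50, the gain is 1.6 to 3.1 points at ICC 0.02 and 6.8 to 14.4 points at ICC 0.10.

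**The case against.** The strongest reply is that an unadjusted primary analysis that respects the randomisation design is valid, that section 7.2 presents the trial as a source of pilot data, and that 7.3.1 already adjusts for strong predictors found imbalanced. Section 7.3.2 even speaks of the primary analysis as having unadjusted and adjusted forms. All of this is true, and it means the plan contains no error here. It does not answer the precision point, because the clause acts only on imbalance and names no variable.

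A reader might infer several stronger things that the documents do not support.
- *That the plan certainly forgoes some 3 to 7 points of power.* By the formula, that range needs a correlation of about 0.43 to 0.66, which no section supplies. A correlation of 0.5 to 0.7 can be made plausible by assuming 50 past visits per physician, but eligibility requires only 2 qualifying patients and section 7.2 assumes 12. Repeat visits by the same patients are also not independent.
- *That 6.1 holds the baseline version of the primary outcome.* It lists a time measure. The outcome in 6.2 is a same-day binary event at a targeted visit, in patients selected for not having been intensified. The measure is a close proxy only.
- *That the data are already extracted, for instance as an 18-month share of above-goal visits intensified.* Section 6.1 describes planned collection and lists no such share. The 18 months in section 3.2.1 concerns blood pressure history.
- *That the measure can never enter the primary model.* The imbalance clause could admit it.

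The reply also notes that the interventions aim to change habitual behaviour, so baseline habit may predict less well in those arms. That stands, and it shrinks the gain (step 6).

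**Conclusion.** The point holds as a cheap improvement. The plan collects a likely predictor of between-physician differences but does not fix it in the primary model, so its precision benefit is lost when the arms are balanced.

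At the plan's inputs, the expected gain is about 0 to 8 points of power for a physician-level correlation of 0 to 0.7, from a base of about 78.5% to 79.5%. That assumes ICC 0.05, 12 patients per physician, two-sided 5% and a similar slope in every arm. Few baseline patients, or prediction confined to control, would bring the gain towards the bottom of the range. The downside is under 1 point. No bias or contradiction is shown.

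**What to change.** In 7.3.1, name one physician-level covariate for the primary GEE: the baseline time-to-treatment-intensification measure listed in 6.1. It should be measured wholly before randomisation and entered whatever the balance. State its look-back window and how it is summarised for each physician, including patients never intensified in the window.

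Because adding a covariate under a logit link makes the odds ratio conditional, also report the arm effect as a standardised risk difference with an interval that respects clustering. This keeps the result on the scale of section 7.2. Keep the model adjusted only for the randomisation design as a sensitivity analysis. The same sentence can tighten the open-ended imbalance clause.

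Cost: one degree of freedom, one derived variable with its definition, and a short addition to 7.3.1. Recruitment, interventions and follow-up are unchanged.
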